5.9.3. Noncompartmental Pharmacokinetic Analysis

Pharmacokinetic parameters of ACE-536 will be derived using noncompartmental analysis method with the software program Phoenix WinNonlin (version 6.2 or higher). The ACE-536 serum concentrations after the first dose (Cycle 1 Day 1 to Cycle 2 Day 1) will be used to estimate the drug serum exposure parameters within the first treatment cycle, and the ACE-536 serum concentrations after the final dose (Cycle 5 Day 1 to end of study), if sufficient, will be used to estimate the terminal elimination half-life in serum. Actual sampling and dosing times will be used in this analysis. The following noncompartmental pharmacokinetic parameters will be estimated:

T_{max}	Time to maximum observed serum concentration, obtained directly from the observed concentration-time data (for the first dose only)
C_{max}	Maximum observed serum concentration, obtained directly from the observed concentration-time data (for the first dose only)
AUC_{21d}	Area under the serum concentration-time curve from Day 1 to Day 21, calculated by the linear trapezoidal method (for the first dose only)
λ_z	Apparent terminal rate constant, calculated by linear regression of the terminal portion of the log-concentration-time curve in serum. Visual assessment may be used to identify the terminal linear phase of the log concentration-time profile. A minimum of 3 data points excluding C_{max} will be used for the calculation. The λ_z will not be estimated if the terminal phase of the log-concentration-time profile does not exhibit a linear decline phase, or if the regression coefficient (Rsq) is less than 0.8 (after the final dose)
$t_{1/2}$	Terminal elimination half-life in serum, calculated as $[(\ln 2)/\lambda_z]$. The terminal elimination half-life will only be calculated when a reliable estimate for λ_z can be obtained (after the final dose)

The following pharmacokinetic parameters will be calculated for diagnostic purposes and listed, but they will not be summarized:

λz lower: lower limit of time (days) included in the calculation of λz

λz upper: upper limit of time (days) included in the calculation of λz

λz N: number of data points used in the calculation of λz

Rsq: regression coefficient of determination for calculation of λz

Additional noncompartmental pharmacokinetic parameters may be determined when appropriate.

5.9.4. Compartmental Pharmacokinetic Analysis

Pharmacokinetic parameters of ACE-536 will also be derived using a one-compartment model with first order absorption and elimination (Phoenix WinNonlin). All ACE-536 serum concentration values obtained from Cycle 1 Day 1 to the end of study will be included in this analysis. Actual sampling and dosing times will be used in this analysis.

The model will be parameterized in terms of the absorption rate constant (k01), apparent clearance (CL/F), and apparent volume of distribution (V/F). Other parameters will be derived from the established model. The main compartmental pharmacokinetic parameters to be estimated are outlined as following:

k01	Absorption rate constant
CL/F	Apparent clearance from the central compartment
V/F	Apparent volume of distribution of the central compartment
T _{max}	Time to maximum serum concentration, calculated as $\ln(k01/k10)/(k01-k10)$, where $k10 = (CL/F)/(V/F)$
C _{max}	Maximum serum concentration for the starting dose, predicted at T _{max}
AUC	Area under the serum concentration-time from time zero to infinity for the starting dose, calculated as (Starting Dose)/(CL/F)
t _{1/2}	Elimination half-life, calculated as $(\ln 2)/k10$

Additional compartmental pharmacokinetic parameters may be determined when appropriate.

5.9.5. Statistical Analysis

All ACE-536 serum concentrations will be listed by dose group, patient, and scheduled time (visit and study day). The ACE-536 serum concentrations will be summarized by dose group and scheduled time, including N (number of observations), arithmetic mean, arithmetic standard deviation (SD), arithmetic coefficient of variation (CV%), geometric mean, geometric CV%, minimum, median, and maximum. Mean (SD) serum concentration-time profiles will be presented on both linear and semilogarithmic scales by dose group for the first 4 weeks. Individual concentration plots will be provided by presenting the observed concentration data along with the one-compartment model-predicted concentration-time profile on the linear scale using actual sampling times and multiple dose data.

Pharmacokinetic parameters will be listed by dose group and patient, and they will be summarized descriptively by dose group (N, mean, SD, minimum, median, maximum, CV%, geometric mean, and geometric CV%). Dose proportionality may be assessed using the exposure data (e.g., C_{max}, AUC) after the first dose.

5.10. Exposure/Response Analysis

The relationship between ACE-536 exposure and Hb and RBC units will be explored.

The exposure endpoint will be AUC for the starting dose. The erythroid response endpoints will include the following depending on study population.

- Patients who are transfusion-free on treatment:
 - Mean of change from baseline in Hb in Week 1-3 (average of weekly Hb measures from Day 7 to 21). This measure represents the initial rate of Hb increase. Patients who receive at least 1 luspatercept dose will be included.
 - Mean of change from baseline in Hb in Week 1-15 (average of weekly Hb measures from Day 7 to 105). Patients who receive at least 3 luspatercept doses will be included.
- Patients with high transfusion burden (requiring ≥ 4 RBC units in 8 weeks at baseline): Change from baseline in RBC units transfused in Week 1-15. Patients who received at least 3 luspatercept doses will be included.

Change in Hb level or RBC unit will be plotted as a function of luspatercept AUC. Linear or nonlinear function may be used to describe the relationship. The relationship may be stratified by baseline EPO levels.

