5. STATISTICAL METHODOLOGY

5.1. Definitions

Low Transfusion Burden (LTB)

LTB patients are defined as those who received < 4 units of RBCs within 8 weeks prior to Cycle 1 Day 1.

High Transfusion Burden (HTB)

HTB patients are defined as those who required ≥ 4 units of RBCs within 8 weeks prior to Cycle 1 Day 1.

Baseline Hemoglobin

Baseline hemoglobin will be an average of hemoglobin measurements within 28 days of Cycle 1 Day 1, excluding measurements within 7 days following RBC transfusion.

Baseline Transfusion Burden

Baseline transfusion burden will be calculated as the total amount of RBC transfusion during the 8 weeks prior to Cycle 1 day 1.

Baseline for Other Parameters

Baseline erythropoietin (EPO) is defined as the maximum test value within 28 days of Cycle 1 Day 1. For all other parameters, baseline is defined as the last observation on or prior to Cycle 1 Day 1.

End of Treatment (EOT)

Procedures and evaluations for the end of treatment visit should be performed on Day 113 (± 7 days) (28 days after the last dose of ACE-536).

Post Treatment Follow-Up (PTFU)

Procedures and evaluations for the post treatment follow-up visit should be performed on Day 141 (± 7 days) (28 days after EOT visit).

End of Study (EOS)

Procedures and evaluations for the end of study visit should be performed on Day 169 (± 7 days) (56 days after the Day 113/EOT visit).

Patients who discontinue treatment early should complete the end of treatment visit at the time of discontinuation and complete the post-treatment follow-up (PTFU) and EOS follow-up visits 28 days (± 7 days) and 56 days (± 7 days) after the EOT visit.

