5.7. Efficacy Analyses

The analyses for all efficacy endpoints will be performed using the ITT population.

All efficacy summaries will be presented by dose cohort for LTB and HTB patients separately. No formal hypothesis testing is planned. In addition, summaries will also be provided for the following group of patients:

- All patients in the ITT population
- Lower dose group includes patients on 0.125, 0.25 and 0.5 mg/kg dose cohorts
- Higher dose group includes patients on 0.75 mg/kg and above

- Patients in the expansion cohorts 1, 2A, 2B, and 3
- Patients in 0.125 to 0.50 mg/kg dose cohorts, and
- Patients in 0.75 to 1.75 mg/kg dose cohorts.

Efficacy Results will also be summarized with the following groups:

- All RS+ patients
- All RS- patients
- RS+ patients in the high dose (≥ 0.75 mg/kg) cohorts, and
- RS- patients in the high dose (≥ 0.75 mg/kg) cohorts.

In general, below rules apply to the derivations of efficacy endpoints related to hemoglobin and RBC transfusion data unless specified otherwise:

- Hemoglobin measurements within 7 days following RBC transfusion will be excluded from efficacy analysis
- For each patient, all efficacy endpoints will be derived based on the last dose + 56 days or the last date from transfusion record data, whichever is earlier.

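### The hemoglobin exposure-response sets in SAP 5.10 are chosen by an on-treatment outcome (no transfusion), which overstates the mean change and can bias the exposure slope in either direction

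*SAP*

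**What the plan says.** SAP 5.10 sets an exploratory aim: "The relationship between ACE-536 exposure and Hb and RBC units will be explored". Exposure is one fixed quantity per patient: "The exposure endpoint will be AUC for the starting dose".

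The response endpoints depend on the patient group:

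- **Hemoglobin.** The group is "Patients who are transfusion-free on treatment". The Week 1-3 endpoint averages weekly changes from Day 7 to 21, with the condition "Patients who receive at least 1 luspatercept dose will be included". The Week 1-15 endpoint averages Day 7 to 105, with the condition "Patients who receive at least 3 luspatercept doses will be included".
- **RBC units.** For patients with high transfusion burden (HTB) at baseline, the endpoint is "Change from baseline in RBC units transfused in Week 1-15", again with at least 3 doses.

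Elsewhere the SAP groups patients by baseline burden. Section 5.1 states: "LTB patients are defined as those who received < 4 units of RBCs within 8 weeks prior to Cycle 1 Day 1". For transfused patients, the general rule in SAP 5.7 removes values, not patients: "Hemoglobin measurements within 7 days following RBC transfusion will be excluded from efficacy analysis". Section 5.10 gives no reason for its restriction and no sensitivity analysis, and the table of changes in SAP 5.15 does not mention it.

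**The concern.** Whether a patient is transfused on treatment is a result of the course of hemoglobin. Protocol 10.2.2 ties transfusion to hemoglobin, through a patient-specific threshold for transfusion-dependent patients and a general 9 g/dL guide with room for symptoms and investigator discretion. Keeping only the untransfused therefore selects on the response that is plotted against exposure.

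Protocol 9.2 says the trial wants to find the lowest safe dose level that gives any erythroid response. SAP 5.10 is the only planned analysis of response against individual exposure. If treatment failures drop out, low exposures look more active than they are, at the end of the range that matters most for that aim. That end is thin: cohorts 1 to 3 hold 3 to 6 patients each, so 9 to 18 in all, including HTB patients.

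**Working it through.** SAP 5.10 states no sample size, slope or precision, so there is no planned figure to reproduce. The check has three parts.

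**1. Who is in each set, as worded**

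| Patient | Hemoglobin set | RBC-unit set |
|---|---|---|
| LTB, never transfused on treatment | yes | no |
| LTB, transfused on treatment | no | no |
| HTB, transfused on treatment | no | yes, if at least 3 doses |
| HTB, becomes transfusion-free | yes | yes, if at least 3 doses |

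The second row is the gap. The transfusion-free condition heads both hemoglobin endpoints and is not limited to the endpoint's own window. A patient with complete Day 7 to 21 values who is first transfused after Day 21 is therefore lost from Week 1-3 as well.

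**2. The 3-dose filter**

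Dose 3 is due on Day 43 and the last permitted dosing day is 85 + 2 = 87 (Protocol, Schedule of Events). A patient who stays on treatment misses dose 3 only if delays exceed about 87 − 43 = 44 days in total. A long hold at hemoglobin of 12 g/dL or more (Protocol Table 4) could do this to a strong responder. Stopping early could do it to a poor one. The documents give no frequency for either.

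**3. Simulations**

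The dose levels (0.125 to 1.75 mg/kg) and the baseline hemoglobin cap of 10 g/dL come from the protocol. All else is assumed:

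- equal numbers at the seven doses
- exposure equal to dose times lognormal variation, CV about 35%
- baseline hemoglobin N(8.7, 0.9), truncated below 10
- average slope 0.8 g/dL per unit of exposure, either common to all or carried by a responder fraction of 30% or 50%.

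*Level of the response.* Change = effect − 0.2 + noise (SD 1.0). Patients whose hemoglobin falls below 7.5, 8.0 or 8.5 g/dL are transfused with probability 0.7 or 1.0. With three response patterns this gives 3 × 3 × 2 = 18 scenarios. The mean dose is 5.705 / 7 = 0.815, so the true mean change is 0.8 × 0.815 − 0.2 = 0.45 g/dL.

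| Quantity | True | Among patients kept |
|---|---|---|
| Mean change, all exposures (g/dL) | about 0.45 | 0.60 to 1.32 |
| Mean change, relative exposure below 0.5 (g/dL) | about 0.0 | 0.18 to 0.64 |

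The rule removed 14% to 48% of patients at low exposure and 4% to 38% at high exposure. The overstatement appeared in all 18 scenarios.

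*Slope.* Hemoglobin was simulated weekly for 15 weeks, with the effect building over 6 weeks, patient SD 0.7 and weekly SD 0.4. Weekly transfusion probability was 0.2 or 0.5 below 7.0, 7.5 or 8.0 g/dL, and each transfusion added 2 g/dL, fading by 15% a week. The 3-dose filter was not applied. Entries are the estimated slope divided by the slope without transfusion, for Week 1-15:

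| Response pattern | Transfusion-free rule | All patients, 7-day exclusion only | All patients, up to first transfusion |
|---|---|---|---|
| Common slope | 0.87 to 0.96 | 0.81 to 0.96 | 0.89 to 0.99 |
| 30% responders | 1.09 to 1.47 | 0.94 to 0.99 | 0.99 to 1.00 |
| 50% responders | 1.04 to 1.23 | 0.89 to 0.98 | 0.95 to 1.00 |

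For Week 1-3, values up to the first transfusion gave 0.96 to 1.00 over all patterns. The transfusion-free rule gave 0.87 to 0.96 with a common slope and 1.05 to 1.46 with the mixtures. In a separate run where transfusion was unrelated to hemoglobin, the ratio was 1.00, so the bias comes from the dependence on outcome.

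**The case against.** **The analysis is exploratory.** It is a plot with an optional fitted function, no hypothesis test is planned, and no primary or secondary response rate uses this set. This stands and limits the severity.

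**The restriction has a reason.** Donor cells raise hemoglobin, so values after a transfusion do not measure drug effect. Three doses is also a sensible minimum for an average to Day 105. Both points stand as grounds for handling post-transfusion values with care and for showing a 3-dose subset. They do not justify dropping values recorded before any transfusion.

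**A reader might infer that the rule flattens the exposure relation.** The documents do not support that. It follows if all patients share one slope. The protocol's sample size section plans around a 30% response rate, and a mixture of responders and non-responders is at least as plausible. It gives a steeper slope.

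**A reader might infer that stopping for lack of effect explains the loss before dose 3.** That route is thin. The hemoglobin example in Protocol 9.4 needs a fall sustained over 8 weeks. Eight weeks is 56 days, and dose 3 is due on Day 43. The other example, becoming transfusion dependent, already fails the transfusion-free condition. The list gives only examples, so other routes remain possible.

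**A reader might infer that the 7-day rule of SAP 5.7 is enough as the remedy.** For Week 1-15 it can leave more bias than the present rule: 0.81 against 0.87 in the worst case run.

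**Conclusion.** The concern holds with modest severity. As worded, SAP 5.10 selects on a post-baseline status that depends on hemoglobin. It leaves transfused LTB patients out of both exposure-response sets and discards complete Week 1-3 data after a later transfusion. The mean change was overstated, and low exposures looked better than they were, in every scenario run. The slope can move either way, by up to 13% too flat or 47% too steep in the weekly runs (1 − 0.87 and 1.47 − 1).

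These sizes rest on assumed slopes, variability and transfusion behavior, none of which the documents give. They also assume equal numbers at each dose, whereas every expansion patient starts at 1.0 mg/kg. They illustrate the mechanism and do not predict the bias in this trial. The effect of the 3-dose filter is unknown in both size and direction.

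**What to change.** In SAP 5.10:

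- Define the hemoglobin set at baseline: all LTB patients with at least 1 dose, for both endpoints.
- For Week 1-3, use all Day 7 to 21 values up to the first transfusion, whatever happens later.
- For Week 1-15, use values up to the first transfusion. Do not rely on the 7-day exclusion alone.
- Keep the transfusion-free set and the set with at least 3 doses as sensitivity plots.
- Report by dose how many patients each filter removes.

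The cost is a change of wording, one changed filter and a small table, with no new data. The downside is that patients transfused early contribute few values, so some flattening of the Week 1-15 slope can remain when transfusion is frequent (0.89 in the worst case run). The report should say so.

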5.7.1. Primary Efficacy Endpoint

The primary efficacy endpoint is the modified erythroid response (mHI-E), defined as below:

- For low transfusion burden (LTB) patients, a hemoglobin increase of ≥ 1.5 g/dL from baseline for ≥ 14 days (in the absence of RBC transfusions). Hemoglobin measurements within 7 days following RBC transfusion will be excluded from analysis.
- For high transfusion burden (HTB) patients, a ≥ 4 units or $\geq 50\%$ reduction in RBC transfusion burden during any rolling 8-week window on treatment compared to baseline. The rolling 8-week window starts on Day 1 and increments by 1 day, e.g., from day 1 to day 56, day 2 to day 57, day 3 to day 58, etc.

A point estimate of the proportion of patients achieving a modified erythroid response will be presented along with its associated exact 95% confidence interval (CI) based on binomial distribution for LTB and HTB patients separately. The complete hemoglobin measurements and RBC transfusion records will be listed for each patient.

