- Dose escalation cohorts and expansion cohort 1 patients only: a bone marrow aspirate must be performed within 21 days after C3D1 (a bone marrow biopsy is not required). Note: A bone marrow aspirate is not required within 21 days after C3D1 for expansion cohort 2 or 3 patients.
- Dose escalation cohorts and expansion cohort 1 patients only: If hemoglobin increases \geq 2 g/dL, an optional bone marrow aspirate can be performed within 7 days of the result.

⁴ **Iron Studies:** Serum iron, TIBC, transferrin, soluble transferrin receptor, NTBI, ferritin.

⁵ **Hematology:** RBC, WBC with differential, hemoglobin, hematocrit, nRBC, reticulocyte count, platelet count, peripheral blasts (on dosing days only: C1D1, C2D1, C3D1, C4D1, C5D1), MCV, MCH, MCHC, and RDW. On dosing days, hemoglobin values are to be drawn and resulted (up to 1 day) prior to dosing (see Section **Error! Reference source not found.**, Patient Dose Modification Rules). Historical hemoglobin data will be collected for 24 weeks, where available, prior to C1D1. During the screening period, hemoglobin will be measured twice; one measure performed within one day prior to Cycle 1 Day 1 and the other performed 7-28 days prior to Cycle 1 Day 1. Neither hemoglobin measure should be influenced by transfusion within 7 days of measurement.

⁶ **Chemistry:** Sodium, potassium, AST, ALT, lactate dehydrogenase (LDH), total bilirubin, direct bilirubin, alkaline phosphatase, blood urea nitrogen (BUN)/urea, creatinine, GGT, calcium, phosphorus, glucose, amylase, lipase, total protein, albumin, and uric acid.

⁷ **Urinalysis by dipstick analysis (local lab):** pH, specific gravity, protein, glucose, ketones, blood, leukocyte esterase, and nitrite, with microscopic examination if indicated. **Urine Chemistry (central lab):** Microalbumin and creatinine.

⁸ **PD Biomarkers:** Hepcidin, GDF15, GDF8, GDF11, and others to be determined.

⁹ **Bone Biomarkers:** BSAP and CTX. Not required for expansion cohort 2 or 3 patients.

¹⁰ **Pregnancy test:** (urine or serum) is required for female patients of child bearing potential at screening and prior to each dose of ACE-536.

¹¹ **Transfusion history** will be collected for 24 weeks, where available, prior to C1D1.

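### SAP 5.10: for high transfusion burden patients, the exposure-response endpoint read with the SAP's only transfusion baseline sets a 15-week count against an 8-week count, with no scaling stated

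*SAP*

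**What the plan says.** SAP 5.10 explores how erythroid response relates to AUC for the starting dose. For HTB patients, identified there as "requiring ≥ 4 RBC units in 8 weeks at baseline", the response is "Change from baseline in RBC units transfused in Week 1-15". The inclusion rule is "Patients who received at least 3 luspatercept doses will be included". The change is to be plotted against AUC, and a linear or nonlinear function may be fitted.

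Section 5.10 does not define the transfusion baseline. SAP 5.1 does: "Baseline transfusion burden will be calculated as the total amount of RBC transfusion during the 8 weeks prior to Cycle 1 day 1". No other transfusion baseline is defined in the SAP.

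Two nearby definitions do not have this difficulty. The hemoglobin responses in 5.10 are means (for Weeks 1-15, "average of weekly Hb measures from Day 7 to 105"), so a longer window does not inflate them. The primary endpoint for HTB patients (5.7.1) is a "reduction in RBC transfusion burden during any rolling 8-week window on treatment compared to baseline", which sets 8 weeks against 8 weeks. HI-E for HTB patients (5.7.2.2) does the same.

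On follow-up, SAP 5.7 says that "all efficacy endpoints will be derived based on the last dose + 56 days or the last date from transfusion record data", whichever is earlier. Section 5.10 does not say whether that cut-off applies to its own endpoints.

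**The concern.** A count of units rises with the length of time over which it is taken. If the Week 1-15 count is set against the 8-week total in 5.1, the change score mixes two things: the change in the patient's transfusion rate, and the extra 7 weeks of counting. The second part is positive for every patient who is still transfused, and it is larger for patients who started with more transfusions.

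What is at stake is the exposure-response display for HTB patients. The vertical axis would have no meaningful zero, and moderate improvement would be drawn as deterioration. Part of the scatter would reflect baseline burden and not response to drug. If baseline burden also differs along the AUC axis, a fitted function would carry that difference as if it were an exposure effect.

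**Working it through.** The plan states no numerical result for this analysis, so there is no figure to reproduce. The check is direct arithmetic on the definitions.

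**Inputs**
- Baseline window: 8 weeks = 56 days (SAP 5.1).
- On-treatment window: Weeks 1-15 = 105 days (SAP 5.10; the end day is taken from the hemoglobin endpoint).
- Smallest HTB baseline: 4 units (SAP 5.1 and 5.10). Larger baselines below are illustrative.
- Assumption: the transfusion rate is constant within each period.

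**Formulas**, with b = units in the 8 baseline weeks and r = the proportional fall in rate on treatment:
- Expected Week 1-15 count = b × (1 − r) × 105/56 = 1.875 × b × (1 − r).
- Literal change = 1.875 × b × (1 − r) − b. With r = 0 this is +0.875 × b, an apparent rise of 87.5% at any baseline.
- Change on a common 8-week scale = count × 56/105 − b = −r × b.

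| b | 15-week count, rate unchanged | Literal change, unchanged | Literal change, 50% fall | Common-scale change, unchanged | Common-scale change, 50% fall |
|---|---|---|---|---|---|
| 4 | 7.5 | +3.5 | −0.25 | 0 | −2 |
| 6 | 11.25 | +5.25 | −0.375 | 0 | −3 |
| 8 | 15 | +7.0 | −0.5 | 0 | −4 |
| 10 | 18.75 | +8.75 | −0.625 | 0 | −5 |
| 12 | 22.5 | +10.5 | −0.75 | 0 | −6 |

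**Break-even.** The literal change is zero when 1.875 × (1 − r) = 1, so r = 1 − 8/15 = 46.7%. Any true reduction below that is plotted as an increase. For example, a 40% fall from 6 units gives 1.875 × 6 × 0.6 − 6 = +0.75.

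**Set against the response definitions.** A sustained drop of 4 units per 8 weeks meets both mHI-E and HI-E for an HTB patient. Its literal change is (b − 4) × 1.875 − b:
- at b = 8, −0.5;
- at b = 10, +1.25;
- at b = 12, +3.0.

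A patient counted as a responder in 5.7 could therefore be plotted as worse in 5.10.

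**Shorter follow-up.** On schedule, the third dose falls on Day 43. If the 5.7 cut-off applies, counting for a patient who stops then ends at Day 43 + 56 = 99 at most, or earlier if the transfusion record ends earlier. At 99 days the artefact is 99/56 − 1 = +76.8% instead of +87.5%. At b = 6 that is +4.61 instead of +5.25 units, a difference of 0.64. A fourth on-schedule dose (Day 64) gives 64 + 56 = 120, which covers all 105 days. This distortion is much smaller than the first, and it makes early stoppers look slightly better.

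**The case against.** Section 5.10 writes no subtraction. The reference there to 8 weeks at baseline identifies the HTB population and does not define the change score, and the section does not use the defined term from 5.1. Transfusion history "will be collected for 24 weeks, where available, prior to C1D1", so a programmer could use a matched 15-week pre-treatment count or a rate. This stands in part: the mismatch is a reading of the text and not an instruction in it. But it is the reading that follows from the SAP's own definitions, and nothing in the SAP directs anyone to a different one.

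Three stronger readings are tempting, and the documents do not support them.

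- **That the sign is wrong for most patients.** The sign reverses only where the true rate falls by more than 0% and less than 46.7%. Larger falls and true worsening keep their sign, and an unchanged patient has no sign to reverse. The documents give no distribution of rate changes, so no proportion can be derived.
- **That a false exposure-response slope will result.** That needs baseline burden to be associated with starting-dose AUC. A route exists: expansion cohorts 2B and 3, starting at 1.0 mg/kg, are capped at 6 units in 8 weeks, and no cap is stated for the escalation cohorts. But expansion cohort 1 also starts at 1.0 mg/kg with no stated cap, and no data on the association are given. Without an association the artefact adds spread and no systematic slope.
- **That the efficacy conclusions are at risk.** The analysis is exploratory, SAP 5.2 and 5.7 plan no formal hypothesis testing, and the documents tie no success criterion to this plot.

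**Conclusion.** The point holds as a defect of definition in one exploratory analysis. Taken with the only transfusion baseline that the SAP defines, the HTB endpoint gives an unchanged patient +0.875 times baseline and shows any rate reduction below 46.7% as an increase. This is more than a missing detail, because applying the stated terms as written yields a wrong value, and the error varies with baseline burden instead of shifting every patient equally.

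The size rests on three assumptions: that the change is formed by subtracting the 5.1 baseline, that the full 105 days are observed, and that the rate is constant within each period. The effect on the AUC relationship is added spread, and distortion of the slope only if baseline burden and starting-dose AUC are associated. Truncated follow-up is a secondary matter: at most 6 days for an on-schedule patient who stops after dose 3, unless the transfusion record ends sooner. The primary mHI-E and HI-E results are not touched.

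**What to change.** State the HTB endpoint in 5.10 on a common time unit: (units transfused in Weeks 1-15) × 56 / (days observed in Weeks 1-15) − baseline units per 8 weeks. An unchanged patient then scores 0 at every baseline. Using days observed also deals with follow-up shorter than 105 days, provided the section says whether the 5.7 cut-off defines those days.

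Percentage change in units per week is an acceptable alternative but not an equivalent one. A true 50% fall is −2, −4 and −6 units at baselines of 4, 8 and 12 on the scaled-difference measure, and −50% at all three on the percentage measure. The percentage also removes the proportionality of response to baseline, so the two would plot differently against AUC. The SAP should choose one and say so. A matched 15-week pre-treatment count would also remove the mismatch, but only for patients whose earlier history is available.

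The cost is one line of SAP text and the matching program code. No new data are needed.
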